2.1. Study Rationale

The efficient community spread of Severe Acute Respiratory Syndrome Coronavirus-2 (SARS-CoV-2) has resulted in the current pandemic of Coronavirus Disease – 2019 (COVID-19), which in severe and critical cases results in progressive pulmonary infection, complicated by respiratory failure, with a high prevalence of acute respiratory distress syndrome. Of all age groups, older adults have the greatest risk of severe COVID-19 and the associated complications (CDC 2020; Grabowski and Mor 2020).

Globally, there are many reports of the rapid spread of COVID-19 amongst residents of skilled nursing facilities following identification of an index case, with high associated rates of morbidity and mortality (Arons et al. 2020; Grabowski and Mor 2020; Graham et al. 2020). In the USA, at least 153,000 residents and employees of nursing homes have contracted COVID-19, accounting for 35% of the country's deaths (Werner et al. 2020). With over 1.3 million residents in nursing home care in the USA (CDC 2016), there is an urgent need for therapeutic strategies to prevent COVID-19 in these populations.

This study aims to evaluate the impact of LY3819253 and LY3819253 in combination with LY3832479 in preventing SARS-CoV-2 infection and COVID-19 in facility staff and residents in skilled nursing and assisted living facilities with a high risk of SARS-CoV-2 exposure.

2.2. Background

The SARS-CoV-2 gains entry to cells through binding of the spike (S) protein to ACE2 receptors on cells (Hoffmann 2020). LY3819253 and LY3832479 are neutralizing immunoglobulin G1 (IgG1) monoclonal antibodies (mAb) to the spike protein of SARS-CoV-2. They are designed to block viral attachment and entry into human cells, and to neutralize the virus. The blocking of viral entry into respiratory cells and viral replication is expected to prevent and/or mitigate the severity of disease in people whom ongoing viral spread and replication is the primary driver of COVID-19 pathophysiology. For those that become infected, the decrease in viral replication may also shorten a patient's extent and duration of viral shedding and transmission, positively impacting public health.

Lilly is evaluating the safety, tolerability, pharmacokinetics (PK), and pharmacodynamics (PD) of LY3819253 in participants hospitalized for COVID-19, in Study J2W-MC-PYAA (PYAA), a randomized, placebo-controlled, double-blind, single ascending dose, Phase 1, first in human study.

Lilly is evaluating the safety, tolerability, PK, and immunogenicity of LY3832479 in healthy participants, in a randomized, placebo-controlled, single dose, Phase 1 study (Study J2Z-MC-PGAA [PGAA]) under IND 150707. Concurrent with Study PGAA, LY3832479 is also under development in China in an ongoing Phase 1 clinical study in healthy participants, Study JS016-001-I. Both studies have started prior to this amendment.

In addition, the impact of LY3819253, alone or in combination with LY3832479, on viral load and clinical outcomes in participants with early mild to moderate COVID-19 illness is being

investigated in Study J2W-MC-PYAB (PYAB), a Phase 2, randomized, double-blind study. Interim analysis from this study suggests treatment with LY3819253 may decrease the risk of hospitalization in patients with mild to moderate COVID-19 (Chen et al. 2020)

Additional information about these studies can be found in the Investigator's Brochure (IB).

2.3. Benefit/Risk Assessment

Anticipated risk is considered low and is based on the known mechanism of action for human derived neutralizing antibodies in acute viral disease states. LY3819253 and LY3832479 consist of a highly specific mAbs directed at foreign (non-human) epitope(s) and will be given to participants at a high risk of SARS-CoV-2 exposure in a controlled setting. The complementarity determining regions of the mAbs were derived from B lymphocytes of 2 individually convalescent naturally SARS-CoV-2-infected patients and, thus, have undergone natural positive and negative selection pressures in vivo, unlike humanized antibodies generated in mice. No clinically relevant off-target binding has been observed in tissue cross reactivity studies of membrane targets in human tissues. Therefore, off-target binding and tissue cross-reactivity are considered unlikely.

A theoretical risk is that these interventions may cause antibody-dependent enhancement (ADE) of viral replication. This is based on responses observed to some monoclonal antibody therapies used in other unrelated viral diseases. Unlike ADE associated with Dengue and Zika virus infections, this phenomenon has not been clearly established for coronavirus infections, such as Severe Acute Respiratory Syndrome (SARS) and Middle East Respiratory Syndrome, and has not been reported to date with SARS-CoV-2. Additionally, limited experience with the use of convalescent serum as a treatment for patients with severe COVID-19 disease has not indicated safety concerns (Shen 2020; Duan 2020).

The risk of clinical ADE for either intervention or in combination is considered low due to

- the structural features of LY3832479, which is engineered to suppress its binding to Fc receptors and C1qm
- the absence of ADE from in vitro studies, and
- the absence of ADE from in vivo nonhuman primate studies for LY3819253.

To date, there is no evidence of productive enhancement of ADE with SARS-CoV-2.

Additional manageable risks associated with most therapeutic monoclonal antibodies are the potential for infusion-related hypersensitivity and cytokine release reactions. The single infusion in this study will be administered at a controlled rate, the study participants will be monitored closely, and adjustments in the infusion rate will be made and/or the infusion stopped, if indicated. Additional information regarding infusion reaction management options is located in Section 6.1.1.2. As of 31 December 2020, approximately 4012 participants received blinded treatment of LY3819253 700 mg, 2800 mg, or 7000 mg, or placebo, of which approximately 3189 participants received LY3819253. Serious infusion-related reactions, including events consistent with anaphylaxis, were reported in these ongoing studies with LY3819253 (FDA EUA fact sheet 2020).

Clinical worsening of COVID-19 after administration of LY3819253 has been reported from post-authorization treatment within 24 hours of infusion. Signs and symptoms may include fever, hypoxia or increased respiratory difficulty, arrhythmia (e.g., atrial fibrillation, sinus tachycardia, and bradycardia), fatigue, and altered mental status. Some of these events required hospitalization. It is not known if these events were related to LY3819253 use or were due to progression of COVID-19.

Combination of LY3819253 and LY3832479

As of 04 November 2020, 542 participants in Study PYAB received blinded treatment of either placebo or the combination of 2800 mg LY3819253 and 2800 mg LY3832479. Three participants reported single immediate non-serious events of pruritis (2 events) and dyspnea (1 event).

Data from Study PYAB interim analysis indicate treatment with LY3819253 or the combination of LY3819253 and LY3832479 may decrease the risk of hospitalization in patients with mild to moderate COVID-19 (Chen et al. 2020; Gottlieb et al. 2020) thus providing benefit to patients with COVID-19.

Given the totality of data on LY3819253 and LY3832479, the well-established safety profile of other therapeutic mAbs, and the lack of disease directed therapeutic options for patients with COVID-19 illness or to prevent the SARS-CoV-2 infection, the overall benefit/risk assessment of this study is considered favorable.

More detailed information about the known and expected benefits and risks and reasonably expected adverse events of LY3819253 and LY3832479 may be found in each respective IB.

3. Objectives and Endpoints

Part 1

To facilitate rapid prophylaxis and treatment of residents and facility staff, participants will be enrolled prior to assessment of baseline SARS-CoV-2 reverse transcription – polymerase chain reaction (RT-PCR) or serology results; thus, multiple analysis populations will exist. This includes separate prevention and treatment analysis populations (defined in the tables below) and baseline serology positive participants.

Safety, pharmacokinetics, and antidrug antibodies will be characterized in the overall intent to treat population and in the analysis populations.

Additional population subset analyses are detailed in Section 9 and/or in the statistical analysis plan.

Prevention Population Objectives and Endpoints
 
Participants negative at baseline for SARS-CoV-2 RT-PCR and serology
 
Comparison Groups: Placebo vs LY3819253 4200 mg
	
Objectives	Endpoints
Primary	

 Compare the incidence of COVID-19 	
 Cumulative incidence of COVID-19 defined as the detection of SARS-CoV-2 by RT-PCR AND mild or worse disease severity^a within 21 days of detection 
 Time frame for endpoint evaluation: 8 weeks from randomization
Key Secondary	

 Compare the incidence of moderate or worse severity COVID-19 	
 Cumulative incidence of moderate or worse severity COVID-19; defined as the detection of SARS-CoV-2 by RT-PCR AND moderate or worse disease severity^a within 21 days of detection 
 Time frame for endpoint evaluation: 8 weeks from randomization

 Compare the incidence of SARS-CoV-2 infection 	
 Cumulative incidence of SARS-CoV-2; defined as the detection of SARS-CoV-2 by RT-PCR 
 Time frame for endpoint evaluation: 4 weeks from randomization
Other Secondary	
[time frame for endpoint evaluation: 8 weeks from randomization]	


 Compare the incidence of SARS-CoV-2 infection Compare the frequency of hospitalization or death due to COVID-19 Characterize clinical status for participants. Compare the mortality due to COVID-19 	
 Cumulative incidence of SARS-CoV-2 infection defined as the detection of SARS-CoV-2 by RT-PCR Proportion of participants who are hospitalized or have died due to COVID-19 Proportion (percentage) of participants who experience these events: 
 COVID-19 related hospitalization (defined as ≥ 24 hours of acute care), COVID-19 related emergency room visit, or death Proportion of participants who die due to COVID-19 (according to the investigator)
Exploratory	
[time frame for endpoint evaluation: 8 weeks from randomization]	

 Compare time to improvement to mild severity symptoms in participants who develop moderate or worse severity^a COVID-19 Characterize COVID-19 illness and severity according to NIAID ordinal scale(s) Characterize SARS-CoV-2 viral endpoints in those participants that become RT-PCR positive Characterize emergence of viral resistance to LY3819253 Compare the duration of hospitalization due to COVID-19 	
 Time to improvement to mild severity^a Worst score on NIAID ordinal scale(s) Proportion of participants that achieve SARS-CoV-2 clearance within 1, 2, or 3 weeks of positive RT-PCR Time to SARS-CoV-2 clearance Comparison from the first positive sample to at least the last positive sample Cumulative days of hospitalization in those who are hospitalized due to COVID-19

Abbreviations: COVID-19 = coronavirus disease – 2019; NIAID = National Institute of Allergy and Infectious Diseases; RT-PCR = reverse transcription – polymerase chain reaction; SARS-CoV-2 = severe acute respiratory syndrome coronavirus 2.

^a As defined in [Table 1](#).

Treatment Population Exploratory Objectives and Endpoints Participants positive at baseline for SARS-CoV-2 RT-PCR and negative at baseline for serology Comparison Groups: Placebo vs LY3819253 4200 mg [time frame for endpoint evaluation: 8 weeks from randomization]	
Objectives	Endpoints

 Compare the frequency of hospitalization or death due to COVID-19 	
 Proportion of participants who are hospitalized or have died due to COVID-19

 Compare the incidence of moderate or worse severity COVID-19 in participants without moderate or worse severity^a COVID-19 at baseline 	
 Cumulative incidence of moderate or worse severity COVID-19, defined as moderate or worse disease severity^a within 21 days of baseline

 Compare the incidence of COVID-19 in participants who are asymptomatic^a baseline 	
 Cumulative incidence of COVID-19; defined as mild or worse disease severity^a within 21 days of baseline

 Compare time to improvement to mild severity symptoms^a in participants who have at baseline, or develop, moderate or worse COVID-19 	
 Time to improvement to mild severity^a

 Characterize clinical status for participants. 	
 Proportion (percentage) of participants who experience these events: 
 COVID-19 related hospitalization (defined as ≥ 24 hours of acute care), COVID-19 related emergency room visit, or death

 Characterize COVID-19 illness and severity according to NIAID ordinal scale(s) 	
 Worst score on a NIAID ordinal scale(s)

 Compare the mortality due to COVID-19 	
 Proportion of participants who die due to COVID-19

 Characterize SARS-CoV-2 viral endpoints 	
 Proportion of participants that achieve SARS-CoV-2 clearance within 1, 2, or 3 weeks of baseline Time to SARS-CoV-2 clearance

 Characterize emergence of viral resistance to LY3819253 	
 Comparison from baseline to at least the last positive sample

 Compare the duration of hospitalization due to COVID-19 	
 Cumulative days of hospitalization in those who are hospitalized due to COVID-19

Abbreviations: COVID-19 = coronavirus disease – 2019; NIAID = National Institute of Allergy and Infectious Diseases; RT-PCR = reverse transcription – polymerase chain reaction; SARS-CoV-2 = severe acute respiratory syndrome coronavirus 2.

^a As defined in [Table 1](#).

Part 2 Prevention

Participants will be tested with point of care SARS-CoV-2 POC test to determine SARS-CoV-2 status. Participants with a negative POC test will randomize to the Prevention Cohort. Those with a positive test will enroll to the Treatment Cohort.

Safety, pharmacokinetics, and antidrug antibodies will be characterized in the overall intent to treat population and in the analysis populations.

Additional population subset analyses are detailed in Section 9 and/or in the statistical analysis plan.

Part 2 Prevention Population Objectives and Endpoints
 
Participant negative on screening Point of Care Test
 
&
 
negative at baseline for SARS-CoV-2 RT-PCR and serology
 
Comparison Groups:
 
 • Placebo vs LY3819253 700 mg • Placebo vs LY3819253 350 mg + LY3832479 700 mg 	
Objectives	Endpoints
Primary	

 • Compare the incidence of COVID-19 	
 • Cumulative incidence of COVID-19 defined as the detection of SARS-CoV-2 by RT-PCR AND mild or worse disease severity^a within 21 days of detection 
 • Time frame for endpoint evaluation: 8 weeks from randomization
Key Secondary	

 • Compare the incidence of moderate or worse severity COVID-19 	
 • Cumulative incidence of moderate or worse severity COVID-19; defined as the detection of SARS-CoV-2 by RT-PCR AND moderate or worse disease severity^a within 21 days of detection 
 • Time frame for endpoint evaluation: 8 weeks from randomization

 • Compare the incidence of SARS-CoV-2 infection 	
 • Cumulative incidence of SARS-CoV-2; defined as the detection of SARS-CoV-2 by RT-PCR 
 • Time frame for endpoint evaluation: 4 weeks from randomization

Other Secondary	
 Characterize the pharmacokinetics of LY3819253 and LY3819253 in combination with LY3832479 Mean concentration of LY3819253 and LY3819253 in the presence of LY3832479 on Day 29 Mean concentration of LY3832479 in the presence of LY3819253 on Day 29
-----------------	--

Abbreviations: COVID-19 = coronavirus disease – 2019; RT-PCR = reverse transcription – polymerase chain reaction; SARS-CoV-2 = severe acute respiratory syndrome coronavirus 2.

^a As defined in [Table 1](#).

Part 2 and Part 3 Treatment Exploratory

For Part 3, results from external, non-study SARS-CoV-2 tests will be used to determine eligibility.

Safety, pharmacokinetics, and antidirug antibodies will be characterized in the overall intent to treat population and in the analysis populations.

Treatment Population Exploratory Objectives and Endpoints Participants positive on screening Point of Care Test (Part 2) & positive at baseline for SARS-CoV-2 RT-PCR and negative at baseline for serology	
[time frame for endpoint evaluation: 4 weeks from randomization]	
Objectives	Endpoints

 Evaluate the frequency of hospitalization or death due to COVID-19 Characterize clinical status for participants. 	
 Proportion of participants who are hospitalized or have died due to COVID-19 Proportion (percentage) of participants who experience these events: 
 COVID-19 related hospitalization (defined as ≥ 24 hours of acute care), COVID-19 related emergency room visit, or death

 Characterize COVID-19 illness and severity according to NIAID ordinal scale(s) Evaluate the mortality due to COVID-19 	
 Worst score on a NIAID ordinal scale(s) Proportion of participants who died due to COVID-19

 Characterize SARS-CoV-2 viral endpoints 	
 Proportion of participants that achieve SARS-CoV-2 clearance within 8 or 29 days of baseline Time to SARS-CoV-2 clearance

 Characterize emergence of viral resistance to LY3819253 or LY3832479 Evaluate the duration of hospitalization due to COVID-19 	
 Comparison from baseline to at least the last positive sample Cumulative days of hospitalization in those who are hospitalized due to COVID-19

Abbreviations: COVID-19 = coronavirus disease – 2019; NIAID = National Institute of Allergy and Infectious Diseases; RT-PCR = reverse transcription – polymerase chain reaction; SARS-CoV-2 = severe acute respiratory syndrome coronavirus 2.

^a As defined in [Table 1](#).

4. Study Design

4.1. Overall Design

Study J2X-MC-PYAD is a randomized, double-blind, placebo-controlled, prophylaxis study to evaluate the efficacy and safety of intravenous LY3819253, alone and in combination with LY3832479, in preventing SARS-CoV-2 and COVID-19, compared to placebo. Skilled nursing and assisted living facilities will serve as the setting to find participants with a high risk of SARS-CoV-2 exposure. The Principal Investigator and site staff may be unaffiliated with the facility.

Residents and facility staff may be included in this study because infected facility staff, who may be asymptomatic, may be important in the spread of SARS-CoV-2 within long term care facilities (Graham et al. 2020). Therefore, providing prophylactic treatment to both residents and facility staff may be highly beneficial in preventing or limiting COVID-19 outbreaks.

An independent Data Safety Monitoring Board Committee (DSMB) will actively monitor interim data to make recommendations about early study closure or changes to sample size (see Section [10.1.5](#), Appendix 1, for more information).

4.1.1. Screening Period

Interested participants or their legal authorized representative will sign the appropriate informed consent document(s) prior to completion of any procedures.

The investigator or qualified designee will review symptoms, risk factors, and other non-invasive inclusion and exclusion criteria prior to any invasive procedures. If the participant is eligible after this review, then site staff will perform the invasive procedures to confirm eligibility.

Part 1:

The screening period for each site opens when a confirmed SARS-CoV-2 index case at the facility is reported to study staff. Screening, randomization and investigational product (IP) administration must be completed within 7 days from reporting of the index case.

Part 2:

Prior to randomization in Part 2, participants will receive a point of care (POC) test for SARS-CoV-2 infection. Participants will be allocated to either Prevention or Treatment Cohorts based on the result. Screening and Day 1 may occur on the same day.

Part 3

The screening period for each participant starts at the signing of the ICF. Screening, randomization, and IP administration must be completed within 7 days from signing the ICF.

4.1.2. Evaluation Period

The evaluation period begins when the participant completes screening and is enrolled in the study. Assessments and procedures will be conducted as described in the SoA (Section [1.3](#)).

Participants in Part 1 will be randomized to placebo or LY3819253. The Sponsor will decide when to trigger activation of Part 2. Activation of Part 2 will be communicated to sites.

Participants in Part 2 will be assigned to a cohort as follows:

- Prevention Cohort: Participants who are SARS-CoV-2 negative during screening on the POC test will be randomized to one of three arms: placebo, LY3819253 700 mg, or LY3819253 350 mg + LY3832479 700 mg.
If enrolling to a placebo-controlled trial is challenged by an effective medication becoming available for prevention of COVID-19 and SARS-CoV-2, then the placebo arm may be dropped.

Note: It is possible that some participants have SARS-CoV-2 negative result on the screening point of care test, but could be positive on the baseline SARS-CoV-2 PCR test. The results from the baseline test will not be available until after the participant is randomized. Once positive results are known from the baseline test, these participants will be unblinded and have the option to continue to be followed for safety according to the Prevention Cohort SoA. Unblinded participants will not be included as part of the defined prevention population

The evaluation period for the Prevention Cohort is 8 weeks, with follow-up to Day 169.

- Treatment Cohort: Participants who test SARS-CoV-2 positive during screening with the POC test will be randomized to one of two arms: LY3819253 700 mg, or LY3819253 700 mg + LY3832479 1400 mg.

The evaluation period for the Treatment Cohort is 4 weeks, with follow-up to Day 85.

Participants in Part 3 will be randomized to LY3819253 700 mg or LY3819253 700 mg and LY3832479 1400 mg. The evaluation period for Part 3 is 4 weeks, with follow-up to Day 85. The Sponsor will decide when to trigger activation of Part 3. Activation of Part 3 will be communicated to sites. Part 3 may be activated prior to Part 2.

Part 2 and Part 3 could be activated concurrently. However, Part 3 will not enroll concurrently with Part 2 at the same facility.

Participants will receive one intravenous infusion of study intervention.

The maximum total duration of study participation for each participant of the prevention groups is 24 weeks. See the SOA for prevention groups in Section 1.3.1.

The maximum total duration of study participation for each participant of the treatment group is 12 weeks. See the SOA for the treatment group in Section 1.3.2.

This table describes the visit types for the prevention population for this study.

Study Day	Activity	Visit Type
0,1	Follow SoA	Onsite
8, 15, 22, 29, 36, 43, 50, 57	Follow SoA Vital signs*	Onsite or Home (Virtual [record collection] if hospitalized)

Daily 2 - 57	Vital signs and symptoms questionnaire daily* Vital signs, clinical status, and concomitant procedures for hospitalized participants.	Onsite or Home (Virtual [record collection] if hospitalized)
ETV and follow-up (85, 141, 169)	Follow SoA	Onsite or Home

*Collected via direct data capture for onsite or home visits only.

This table describes the visit types for the treatment population for this study.

Study Day	Activity	Visit Type
0, 1	Follow SoA	Onsite
8, 29	Follow SoA Vital signs*	Onsite or Home (Virtual [record collection] if hospitalized)
Daily 2-29	Vital signs, clinical status, and concomitant procedures for hospitalized participants.	Virtual (record collection) if hospitalized
ETV and follow-up (85)	Follow SoA	Onsite or Home

*Collected via direct data capture for onsite or home visits only.

Hospitalization

If a participant is hospitalized, efforts will be made to retrieve hospital records and report procedures and assessments according to the SoA, as feasible.

Definitions for COVID-19 Severity

This table gives the definitions for COVID-19 severity of illness for those participants who are SARS-CoV-2 positive as determined by standard RT-PCR assay or equivalent test.

Table 1 Definitions for COVID-19 Severity

Severity	Description
Mild	Mild symptoms that could include: 
 fever, cough, sore throat, malaise, headache, muscle pain, gastrointestinal symptoms, without shortness of breath or dyspnea AND No clinical signs indicative of Moderate, Severe, or Critical Severity
Moderate	Symptoms of moderate illness with COVID-19, which could include any symptom of mild illness or shortness of breath with exertion AND Clinical signs suggestive of moderate illness with COVID-19, such as: 
 respiratory rate \geq 20 breaths per minute,

	
 • heart rate \geq 90 beats per minute • O2 utilization increase of \geq 1L/min (for participants receiving O2 at baseline)* • IV fluid initiation* 
AND no clinical signs indicative of Severe or Critical Illness Severity

Severe	
Symptoms suggestive of severe systemic illness with COVID-19, which could include any symptom of moderate illness or shortness of breath at rest, or respiratory distress
 
AND Clinical signs indicative of severe systemic illness with COVID-19, such as
 
 • respiratory rate \geq 30 breaths per minute, • heart rate \geq 125 beats per minute, • SpO2 \leq 93% on room air at sea level or PaO2/FiO2 $<$ 300 
AND No clinical signs indicative of Critical Illness Severity

Critical	
Evidence of critical illness, defined by at least one of the following:
 
 • Respiratory failure defined based on resource utilization requiring at least one of the following: 
 • endotracheal intubation and mechanical ventilation, • oxygen delivered by high-flow nasal cannula (heated, humidified, oxygen delivered via reinforced nasal cannula at flow rates $>$ 20 L/min with fraction of delivered oxygen \geq 0.5), • noninvasive positive pressure ventilation, • extracorporeal membrane oxygenation (ECMO), or • clinical diagnosis of respiratory failure (i.e., clinical need for one of the preceding therapies, but preceding therapies not able to be administered in setting of resource limitation) • Shock • Multi-organ dysfunction/failure
Death	

Abbreviations: COVID-19 = coronavirus disease – 2019; FiO2 = fraction of inspired oxygen in the air; IV = intravenous; PaO2 = partial pressure of oxygen; SpO2 = saturation of peripheral oxygen.

Adapted from FDA 2020.

*Addition to FDA Guidance applies only to residents at skilled nursing and assisted living facilities.

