8.1.2. Participant Symptoms Questionnaire

Participants will be asked about the presence or absence of symptoms and signs associated with COVID-19 experienced during the past 24 hours, at the timepoints described in the SoA.

Signs and symptoms associated with COVID-19 should not be captured as AEs, unless more severe than expected. See Section 10.3.1. for additional information AE definitions used in this study.

Symptoms include

- shortness of breath with movement
- shortness of breath at rest
- cough
- chest pain or discomfort with breathing
- feeling feverish
- chills
- sore throat
- muscle or body aches and pain
- fatigue or loss of energy
- headache
- nausea
- diarrhea
- vomiting
- loss of appetite
- loss of taste, and
- loss of smell.

Participants requiring a legally authorized representative to provide signed informed consent will not be asked to report the presence or absence of symptoms. Only symptoms that may be observed by site staff other than the participant will be recorded, including

- shortness of breath with movement
- shortness of breath at rest
- cough
- diarrhea, and
- vomiting.

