9.4.5. Primary Endpoint

The endpoint for the primary analysis in the prevention populations is defined as cumulative incidence of COVID-19, defined as the detection of SARS-CoV-2 by RT-PCR AND mild or worse disease severity within 21 days of detection, up to 8 weeks after randomization.

The primary analysis model will be a logistic regression model which will include occurrence of a primary endpoint event as the response variable, and treatment and stratification factors such as facility as explanatory variables.

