### ***6.3.2. Missing COVID-19 Status or Disease Severity***

For the primary and key secondary endpoints, if a participant has at least one post-baseline RT-PCR test result and has not yet met the criterial for COVID-19 or is missing data used to determine COVID-19 status, the participant will be treated as not experiencing COVID-19. The same logic will be used for moderate-or-worse severity COVID-19.

As a supplementary analysis on these endpoints, the approach described in Section [6.3.1](#) will be used to handle missing COVID-19 status or disease severity due to death unrelated to COVID-19, study discontinuation, or the triggering of the Primary Database Lock. Participants with missing information will be treated as not experiencing the associated endpoint event and will be weighted based on the proportion of the Evaluation Period that was completed.

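### Table 1 has no severity level for an RT-PCR-positive participant with shortness of breath and no clinical sign, so a case that stays in that state is scored as a primary-endpoint non-event

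*Protocol*

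**What the plan says.** Protocol 9.4.5 sets COVID-19 over the 8 weeks from randomization as the primary endpoint, "defined as the detection of SARS-CoV-2 by RT-PCR AND mild or worse disease severity within 21 days of detection". Severity comes from Protocol Table 1 in Section 4.1.2.

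- **Mild:** the listed symptoms, "without shortness of breath or dyspnea AND No clinical signs indicative of Moderate"; signs of the two levels above that are excluded as well.
- **Moderate:** a mild symptom or "shortness of breath with exertion AND Clinical signs suggestive of moderate illness with COVID-19, such as" the thresholds that follow. Symptom and sign are joined by AND.
- **Severe:** symptoms, which may include shortness of breath at rest, "AND Clinical signs indicative of severe systemic illness with COVID-19, such as" the thresholds that follow.
- **Critical:** respiratory failure, shock or multi-organ dysfunction.

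The SAP adds no derivation of its own; its objective tables point back to Table 1. SAP 6.3.2 supplies the default. For a participant with at least one post-baseline RT-PCR result who has not met the COVID-19 criteria, "the participant will be treated as not experiencing COVID-19".

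**The concern.** Severity levels that feed a mild-or-worse endpoint should be exhaustive for symptomatic infection and should not fall as symptoms get worse. Table 1 fails on both counts in one place. Shortness of breath excludes Mild, but it does not reach Moderate or Severe without a sign. Adding breathlessness to a cough can therefore turn a primary event into a non-event.

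What is at stake is the meaning of the primary endpoint. It is presented as COVID-19 of any symptomatic severity, yet it would omit some infected participants whose symptoms go beyond those of the Mild row. There is also a reproducibility problem. With no stated rule for cases that fit no level, two programmers could reach different primary event counts, and a choice made after unblinding would be post hoc.

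**Working it through.** **1. Table 1 applied literally.** All participants below are RT-PCR positive with no critical illness. No sign means no clinical sign of any kind.

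| Recorded state | Mild | Moderate | Severe | Result |
|---|---|---|---|---|
| Cough only, no sign | met | no sign | no sign | primary event |
| Exertional breathlessness, with or without cough, no sign | barred | no sign | no sign | no level |
| Breathlessness at rest, with or without cough, no sign | barred | no sign | no sign | no level |
| Cough and exertional breathlessness, moderate sign | barred | met | no severe sign | primary event |

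Rows two and three are the gap: four symptom combinations in all. Literal coding also leaves some other states without a level. An infection with no symptom and no sign is correctly left out. A sign with no recorded symptom, and breathlessness at rest as the only symptom with a moderate sign, depend on how the rows are read and are not part of this point.

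**2. Whether anything closes the gap.** Neither document has a tie-break, an adjudication step or a programmed classification rule. SAP 6.10.2 varies the model, the effect scale and the population. The sensitivity analysis in SAP 6.10.3.1 varies when moderate disease may occur. The weighting in SAP 6.3.1 and 6.3.2 deals with incomplete follow-up. None of these reclassifies an unassigned case, so the SAP 6.3.2 default applies.

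**3. The plan's event number.** Inputs from Protocol 9.2, Part 1: two-sided 0.05, 90% power, placebo rate 4.0% for moderate or worse disease, risk ratio 0.33. Allocation is 1:1 (Protocol 6.3). Schoenfeld: events = 4 × (1.960 + 1.282)² / (ln ratio)².

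- Ratio 0.33: 34.2, rounded up to 35.
- Odds ratio implied by 4.0% and 4.0% × 0.33 = 1.32%, which is 0.321: 32.6, rounded up to 33.

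The stated 33 is reproduced to within rounding and the choice of ratio. Power at 33 events with ratio 0.33 is 89.0%.

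**4. What lost cases would do.** The documents give no frequency for the gap, so the shares below are assumptions. If the primary endpoint had only 33 true events:

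| Assumed share lost | Events left | Power |
|---|---|---|
| 2% | 32.3 | 88.3% |
| 5% | 31.4 | 87.4% |
| 10% | 29.7 | 85.6% |
| 20% | 26.4 | 81.3% |

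Observed risk ratio = 0.33 × (1 − share lost on active) / (1 − share lost on placebo).

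- Equal loss: 0.33, unchanged.
- 10% placebo, 5% active: 0.33 × 0.95 / 0.90 = 0.348.
- 5% placebo, 10% active: 0.33 × 0.90 / 0.95 = 0.313.
- 5% placebo, 20% active: 0.33 × 0.80 / 0.95 = 0.278.

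**5. Lock triggers (SAP 6.1.5).** The main triggers are 33 moderate-or-worse cases in Part 1 and 56 in Part 2. Each such case is also a primary event, so the primary endpoint has at least those numbers whatever the gap removes. The Part 1 fallback trigger is 36 infections within 4 weeks, with only the primary endpoint then evaluated. Unless later infections add events, 33 primary events would need 33/36 = 91.7% of those infections to be classified as mild or worse. That is not guaranteed, so lost cases could cost power there.

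**The case against.** The strongest reply is that the gap is small. Several parts of that reply stand.

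- The sign lists in Moderate and Severe are given as examples. A reader might infer that anyone breathless who misses the listed thresholds is lost. The text does not support that: an unlisted sign could still place the participant in Moderate or Severe. The gap is breathlessness with no sign at all.
- A reader might infer that a non-event is automatic. It is not. Symptoms and vital signs are collected daily to Day 57, and severity counts at any time within 21 days of detection. One day with a mild symptom and neither breathlessness nor a sign makes the case an event. So does one day with a symptom plus, for example, a respiratory rate of at least 20 or a heart rate of at least 90.
- A reader might infer that the loss is greatest in participants consented through a representative. For them, Protocol 8.1.2 says "Only symptoms that may be observed by site staff other than the participant will be recorded", and two of the five items named are shortness of breath. But those are counts of items, not of cases. The Schedule of Activities also has a separate daily row for the Table 1 symptoms and interventions, and temperature is measured daily. The documents hold no data that locate the loss in this group.
- A sign with no symptom also fits no level, but that exclusion may be deliberate in an endpoint meant to capture symptomatic disease. It is not shown to be an error.
- These infections still count in the SARS-CoV-2 infection endpoints if detected in the relevant windows.

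Double blinding argues against biased recording. It does not rule out unequal loss, because a treatment that changes severity could move cases into or out of the gap. The documents show neither the direction nor the size of any such shift.

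None of this supplies a level for a participant who stays breathless without a sign.

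**Conclusion.** The concern holds in this limited form. Table 1 assigns no level to RT-PCR-positive participants with shortness of breath and no clinical sign. Where that persists on every symptomatic day of the 21-day window, the stated rules score a non-event for a participant who would have been an event with cough alone. This rests on reading the AND in Moderate and Severe as written and on the SAP 6.3.2 default.

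The gap is probably narrow, and its frequency cannot be derived from the documents; the losses shown are illustrations only. It would be wrong to conclude that planned power is lost: the main triggers protect it, and equal loss leaves the risk ratio at 0.33. The defect is one of endpoint validity, with possible loss of events only under the Part 1 fallback trigger. It merits correction because the primary endpoint is affected and the remedy is simple.

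**What to change.** Before unblinding, add one counting rule to SAP 6.10.1. It applies to any RT-PCR-positive participant with at least one recorded COVID-19 symptom, shortness of breath included, within 21 days of detection who fits no Table 1 level. That participant counts as mild or worse for the primary endpoint. Report the primary result with and without these cases. The rule should govern counting only and leave the Mild row's label as it is. An analysis of signs without symptoms is optional.

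The cost is a sentence in the SAP and a few lines of programming; the symptoms and vital signs are already collected. A matching note to Protocol Table 1 may be needed, and Protocol 9.4 calls for an amendment if the change is judged to alter a principal feature. The downside is a slight departure from the literal Mild row. The rule could also count long-standing breathlessness in an otherwise silent infection, much as Table 1, which states no new-onset requirement, could already count a long-standing cough. The paired report shows how much depends on it.
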